3.9.2. Clinical Laboratory Parameters

Laboratory parameters will be presented in conventional (ie, US) units. Unless specified otherwise, only scheduled laboratory parameters will be included in the summaries.

All laboratory data, including those collected at unscheduled visits, will be included in the listings.

Laboratory results (baseline and change from baseline) for the Safety Population during Double-blind Treatment Period for chemistry and hematology parameters will be summarized by treatment group and by visit.

The number (percentage) of subjects with potentially clinically significant (PCS) values at any postbaseline visit, will be summarized by treatment group. PCS criteria are presented in [Table 1](#). The denominator will be all subjects with non-PCS baseline and at least one postbaseline assessment in the Safety Population and the numerator will be the number of subjects with non-PCS baseline and PCS at postbaseline. All PCS values including baseline PCS values will be included in supportive listings.

For selected metabolic parameters (fasting total cholesterol, fasting HDL, fasting LDL, fasting triglycerides, fasting glucose, and HbA1c), an analysis of sustained PCS values will also be conducted. The percentage of subjects with sustained PCS values through the treatment period will be summarized. The denominator is all subjects with non-PCS at baseline and at least two postbaseline assessments, and the numerator is the number of subjects who met PCS criteria at the last 2 assessments within the treatment period.

Shift tables for metabolic parameters (fasting total, fasting HDL, fasting LDL cholesterol, fasting triglycerides, fasting glucose, and HbA1c) and liver function tests will be presented. The criteria are summarized in [Table 2](#), [Table 3](#), [Table 4](#) and [Table 5](#).

A listing of subjects who met Hy's Law will be provided. Subjects who met Hy's Law is defined as subjects who meet all of the following three criteria:

1. Alanine aminotransferase (ALT) or aspartate aminotransferase (AST) $\geq 3 \times$ upper limit of normal (ULN)
2. Total bilirubin $\geq 2 \times$ ULN
3. A non-elevated alkaline phosphatase (ALP) $< 2 \times$ ULN

Table 1: Criteria of Potentially Clinically Significant (PCS) Abnormality for Selected Analytes

Parameter	Criteria
Chemistry	
Albumin	<2.5 g/dL
Alkaline Phosphatase (U/L)	$\geq 3 \times \text{ULN}$
Alanine Aminotransferase (U/L)	$\geq 3 \times \text{ULN}$

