Aspartate Aminotransferase (U/L)	$\geq 3 \times \text{ULN}$
Bilirubin, Total	$\geq 2.0 \text{ mg/dL}$
Blood Urea Nitrogen	$>30 \text{ mg/dL}$
Cholesterol, Random	$>300 \text{ mg/dL}$
Cholesterol, Fasting	$\geq 240 \text{ mg/dL}$
Cholesterol, HDL Fasting	$\leq 40 \text{ mg/dL}$
Cholesterol, HDL Fasting	Decrease $\geq 20 \text{ mg/dL}$
Cholesterol, LDL Fasting	$\geq 160 \text{ mg/dL}$
Cholesterol, LDL Fasting	Increase $\geq 30 \text{ mg/dL}$
Creatine Kinase (U/L)	$\geq 3 \times \text{ULN}$
Creatinine	$\geq 2.0 \text{ mg/dL}$
Glucose, Random	$<50 \text{ mg/dL}$ or $\geq 200 \text{ mg/dL}$
Glucose, Fasting	$<50 \text{ mg/dL}$ or $\geq 126 \text{ mg/dL}$
Glucose, Fasting	Increase $\geq 10 \text{ mg/dL}$
HbA1c	$\geq 5.7\%$
Potassium	$<3 \text{ mmol/L}$ or $>5.5 \text{ mmol/L}$
Lactate Dehydrogenase (U/L)	$>3 \times \text{ULN}$
Prolactin (Female)	$>30 \text{ ng/mL}$
Prolactin (Male)	$>20 \text{ ng/mL}$
Prolactin (Female)	$>3 \times \text{ULN}$
Prolactin (Male)	$>3 \times \text{ULN}$
Sodium	$<130 \text{ mmol/L}$ or $>150 \text{ mmol/L}$
Triglycerides, Fasting	$\geq 200 \text{ mg/dL}$
Triglycerides, Fasting	Increase $\geq 50 \text{ mg/dL}$

Table 1: Criteria of Potentially Clinically Significant (PCS) Abnormality for Selected Analytes (Continued)

Parameter	Criteria
Hematology	
Hematocrit (Female)	$\leq 32\%$
Hematocrit (Male)	$\leq 37\%$
Platelets	$< 75.0 \times 10^3 \text{ cells}/\mu\text{L}$ or $\geq 700.0 \times 10^3 \text{ cells}/\mu\text{L}$
Leukocytes	$\leq 2.8 \times 10^3/\mu\text{L}$ or $\geq 16.0 \times 10^3/\mu\text{L}$
Neutrophils, Absolute	$< 1.5 \times 10^3/\mu\text{L}$ $< 1.0 \times 10^3/\mu\text{L}$

Abbreviations: HDL= high-density lipoprotein; LDL=low-density lipoprotein; ULN=upper limit of normal.

Table 2: Shifts Category from Baseline to Any Postbaseline for Selected Lipid Parameters

Parameter	Shift Criterion
Total cholesterol (fasting) mg/dL	Normal (< 200) to borderline (≥ 200 and < 240)
	Borderline (≥ 200 and < 240) to high (≥ 240)
	Normal (< 200) to high (≥ 240)
LDL cholesterol (fasting) mg/dL	Normal (< 100) to borderline (≥ 100 and < 160)
	Borderline (≥ 100 and < 160) to high (≥ 160)
	Normal (< 100) to high (≥ 160)
HDL cholesterol (fasting) mg/dL	Normal (≥ 40) to low (< 40)
Triglycerides (fasting) mg/dL	Normal (< 150) to borderline (≥ 150 and < 200)
	Borderline (≥ 150 and < 200) to high (≥ 200)
	Normal (< 150) to high (≥ 200)

Abbreviations: HDL=high-density lipoproteins; LDL=low-density lipoproteins.

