3.9.3. Vital signs and Electrocardiograms

3.9.3.1. Vital Signs

Descriptive statistics for vital signs and changes from baseline values at each scheduled time point will be presented by treatment group for the double-blind period.

Vital sign values will be considered PCS if they meet both the observed-value criteria and the change from-baseline criteria listed in [Table 6](#). The number and percentage of subjects with PCS postbaseline values will be tabulated by treatment group for the Double-blind Treatment Period. The percentages will be calculated relative to the number of subjects with available non-PCS baseline values and at least 1 postbaseline assessment for the double-blind period. The numerator will be the total number of subjects with available baseline values and at least 1 PCS postbaseline value for double-blind period. A supportive tabular display of subjects with PCS postbaseline values will be provided, including the subject ID number, and baseline and all postbaseline (including non-PCS) values.

All vital signs will be presented in the subject data listing.

Table 6: Criteria for Potentially Clinically Significant (PCS) Blood Pressure or Pulse Rate

Parameter	Criteria
Supine Systolic Blood Pressure	≤ 90 and decrease ≥ 20 mm Hg ≥ 180 and increase ≥ 20 mm Hg
Supine Diastolic Blood Pressure	≤ 50 and decrease ≥ 15 mm Hg ≥ 105 and increase ≥ 15 mm Hg
Supine Heart Rate	≤ 50 and decrease ≥ 15 bpm ≥ 120 and increase ≥ 15 bpm

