3.9.3.2. Electrocardiograms

Descriptive statistics for ECG parameters (heart rate, PR interval, RR interval, QRS interval, QT interval, and QTc interval) at baseline and change from baseline values at the end of the Double-blind Treatment Period will be presented by treatment group. QTc interval will be calculated using Fridericia ($QTcF = QT/(RR)^{1/2}$) corrections; if RR is not available, it will be replaced with 60/HR in the correction formula.

Electrocardiogram parameter values are considered PCS if they meet or exceed the higher-limit PCS criteria listed in Table 7. The number and percentage of subjects with PCS postbaseline ECG values will be tabulated by treatment group for the Double-blind Treatment Period. The percentages will be calculated relative to the number of subjects with non-PCS baseline values and at least 1 postbaseline assessment for the Double-blind Treatment Period. The numerator is the total number of subjects with non-PCS baseline values and at least 1 PCS postbaseline value for the Double-blind Treatment Period. A supportive tabular display of subjects with PCS postbaseline values will be provided, including the subject ID number, study center number, the baseline value, all postbaseline (including non-PCS) values, and change from baseline.

Table 7: Criteria for Potentially Clinically Significant (PCS) QTcF

Parameter	Criteria
QTcF	>450 to ≤ 480 msec
	>480 to ≤ 500 msec
	>500 msec
	Change from baseline >30 to ≤ 60 msec
	Change from baseline >60 msec

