6.1. Analysis Visit Windows

Scheduled analysis visits are visits upon scheduled time points as specified in the protocol ([Table 3 Schedule of Visits and Assessments](#)).

Scheduled analysis visits during the study period will be the same as the nominal visits collected in the eCRF. There will be one valid value of assessment kept for each scheduled analysis visit in summary/ analysis statistics.

Unscheduled visits are visits with data not collected on the scheduled time point. Unscheduled visits will not be used for by-visit summary/analysis statistics unless specified otherwise.

All unscheduled visit data as collected in eCRFs will be included in listings.

Last postbaseline values are defined as the last valid postbaseline values collected for each subject during the Double-blind Treatment Period.

An early termination (ET) visit during the on-treatment period can be mapped to a scheduled visit, if there is no valid value already at that visit. Visit windows are defined for CGI, weight or body composition related endpoints ([Table 9](#)), laboratory assessments ([Table 10](#)), IWQOL-Lite ([Table 11](#)), vital sign ([Table 12](#)) and ECG ([Table 13](#)). An ET visit that is not mapped will not be summarized in the tables or figures, but will be included in the listing.

Table 9: Visit Window for Efficacy and Safety Assessments for CGI, Body Weight, Waist Circumference and Body Composition

Analysis Visit to be Mapped to	Target Study Week	Target Visit Day ^a	Visit Window
Visit 3	Week 1	Day 8	[2, 11]
Visit 4	Week 2	Day 15	[12, 21]
Visit 5	Week 4	Day 29	[22, 35]
Visit 6	Week 6	Day 43	[36, 49]
Visit 7	Week 8	Day 57	[50, 63]
Visit 8	Week 10	Day 71	[64, 77]
Visit 9	Week 12	Day 85	[78, 91]

^a Visit Day is calculated as date of visit – date of the first dose of study drug + 1 day.

Table 10: Visit Window for Laboratory Assessments

Analysis Visit to be Mapped to	Target Study Week	Target Visit Day	Visit Window
Visit 4	Week 2	Day 15	[2, 50]
Visit 9	Week 12	Day 85	[51, 91]

Table 11: Visit Window for IWQOL-Lite

Analysis Visit to be Mapped to	Target Study Week	Target Visit Day	Visit Window
Visit 5	Week 4	Day 29	[2, 57]
Visit 9	Week 12	Day 85	[58, 91]

Table 12: Visit Window for Vital Sign

Analysis Visit to be Mapped to	Target Study Week	Target Visit Day	Visit Window
Visit 4	Week 2	Day 15	[2, 28]
Visit 6	Week 6	Day 43	[29, 63]
Visit 9	Week 12	Day 85	[64, 91]

Table 13: Visit Window for ECG

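### SAP 6.1 keeps unmapped on-treatment early-termination (ET) values out of every table, which conflicts with PCS and laboratory shift tables defined on any postbaseline value; ECG is the main case

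*SAP*

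**What the plan says.** Protocol 7.3 asks subjects who stop treatment early to attend an ET visit close to the last dose, with the same assessments as Visit 9. Those include an ECG, laboratory tests and vital signs.

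SAP 6.1 says that an ET visit in the on-treatment period "can be mapped to a scheduled visit, if there is no valid value already at that visit". Tables 10, 12 and 13 give the windows for laboratory tests, vital signs and ECG. For the remainder: "An ET visit that is not mapped will not be summarized in the tables or figures, but will be included in the listing". The same section also has this definition: "Last postbaseline values are defined as the last valid postbaseline values collected for each subject during the Double-blind Treatment Period".

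The safety tables are defined more broadly:

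- **All three assessments:** Protocol 14.6 counts subjects who meet PCS criteria at any visit after baseline.
- **ECG:** the SAP 3.9.3.2 numerator is "subjects with non-PCS baseline values and at least 1 PCS postbaseline value for the Double-blind Treatment Period".
- **Vital signs:** the SAP 3.9.3.1 numerator is subjects with "available baseline values and at least 1 PCS postbaseline value for double-blind period".
- **Laboratory tests:** SAP 3.9.2 counts PCS values at any postbaseline visit. The shift tables run to any postbaseline value, as in the Table 2 title: "Shifts Category from Baseline to Any Postbaseline for Selected Lipid Parameters". Only laboratory tests have shift tables.

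**The concern.** Both instructions cannot be followed as written. An on-treatment ET value is planned, observed and postbaseline, so it belongs in a table defined on any postbaseline value. SAP 6.1 nevertheless bars it from every table if its day falls in no window, or if the scheduled visit for that window already has a value.

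The values at risk come from subjects who stop early, and safety and tolerability is the secondary objective. An abnormality first seen at the ET visit could be missing from the table meant to count it. For ECG, the whole subject could be missing.

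**Working it through.** The plan states no figure for this point, so there is none to reproduce. The check has two steps: which ET days cannot be mapped, and how many visits that might be.

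**Step 1: unmapped days.** Inputs are the windows and target days in SAP Tables 10, 12 and 13. Scheduled visits are assumed to take place on target and to give valid values.

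| Assessment | Postbaseline windows (target day) | Unmapped ET days | Reason | Subject's place in the PCS table |
|---|---|---|---|---|
| ECG | 64–91 (85) | up to 63 | no window exists | leaves numerator and denominator |
| Laboratory | 2–50 (15); 51–91 (85) | 16–50 | Week 2 value already fills the window | stays in denominator on the Week 2 value |
| Vital signs | 2–28 (15); 29–63 (43); 64–91 (85) | 16–28 and 44–63 | Week 2 or Week 6 value already fills the window | stays in denominator on earlier values |

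The schedule (Protocol Table 3) has no ECG between screening and Visit 9/ET, so the ET ECG is normally the only postbaseline one. The ECG entry in the last column holds if SAP 6.1 governs the PCS denominator.

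**Step 2: illustrative counts.** From the documents: 35% cumulative dropout, 400 subjects in the efficacy population and about 425 randomized (SAP 2). Assumed: dropout uniform over 84 days, ET on the dropout day and on treatment, ET attendance of 50% to 100%.

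- ET visits attended: low 0.35 × 0.5 × 400 = 70; high 0.35 × 1.0 × 425 = 148.75.
- ECG: 63/84 = 0.750. 0.750 × 70 = 52.5; 0.750 × 148.75 = 111.6.
- Laboratory: 35/84 = 0.417. Low 29.2; high 62.0.
- Vital signs: (13 + 20)/84 = 33/84 = 0.393. Low 27.5; high 58.4.

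Starting at Day 2 instead of Day 1 lowers the ECG upper figure only to 62/84 × 148.75 = 109.8.

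**Sensitivity to dropout timing.** Share of ET visits excluded, with dropout density rising or falling linearly over 84 days:

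| | Late-weighted | Uniform | Early-weighted |
|---|---|---|---|
| ECG | (63/84)² = 56% | 75% | 1 − (21/84)² = 94% |
| Laboratory | (50² − 15²)/84² = 32% | 42% | (69² − 34²)/84² = 51% |
| Vital signs | (28² − 15² + 63² − 43²)/84² = 38% | 39% | (69² − 56² + 41² − 21²)/84² = 41% |

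**Direction.** For laboratory tests and vital signs, an unmapped subject already has a value and so is already in the denominator. Adding the ET value can turn a non-case into a case but not the reverse, so any-visit PCS counts are unchanged or too low as planned. For ECG, numerator and denominator lose the same subjects, so the direction is unknown.

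**The case against.** The strongest reply is that the SAP 6.1 sentence belongs to a section on visit windows and was meant only for by-visit summaries. On that reading the specific safety sections govern, and a subject with only an ET ECG counts under SAP 3.9.3.2. The definition of a last postbaseline value in SAP 6.1 also suggests that ET values were meant to be used somewhere. The dataset specifications, programming specifications and mock tables are separate documents that were not available and might settle it.

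That reading is possible, but the text does not secure it. SAP 6.1 limits its exclusion of unscheduled visits to by-visit statistics and puts no such limit on unmapped ET visits. For laboratory data, SAP 3.9.2 may point the same way: "Unless specified otherwise, only scheduled laboratory parameters will be included in the summaries". Programming documents should implement the SAP, and cannot be assumed to override an explicit exclusion.

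The objections to weight stand. The tables are descriptive. Unmapped ET visits are listed, laboratory PCS values go into supportive listings, and Hy's Law cases are reported as a listing. Clinically significant laboratory values are also recorded as adverse events (Protocol 13.1).

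A reader might infer more than the documents support:

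- **Bias between arms.** This would depend on dropout timing and ET attendance by arm, which the documents do not give.
- **Sustained PCS must change too.** Of that analysis the SAP says: "The denominator is all subjects with non-PCS at baseline and at least two postbaseline assessments". A subject with only a Week 2 value therefore drops out. Requiring a later laboratory value before calling an abnormality sustained is a defensible choice, since a Week 2 value and an ET value days later say little about persistence.
- **Leaving unscheduled values out of PCS tables is an error.** SAP 7 makes that choice explicitly. It is narrower than Protocol 14.6, but it is a choice.

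**Conclusion.** The conflict is real and should be resolved. Followed as written, SAP 6.1 removes planned on-treatment ET values from tables that the protocol and SAP define on any postbaseline value. ECG is the main case, because QTcF tables would describe only subjects with an ECG at Day 64 or later. Laboratory and vital-sign PCS counts can only be unchanged or understated.

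Under the assumptions above, about 53 to 112 ET ECGs, 29 to 62 laboratory sets and 28 to 58 vital-sign sets would be excluded. No change in any PCS percentage has been estimated. Attendance below 50%, or ET visits that fall off treatment, would reduce the counts, so the lower ends are not lower bounds. Body weight has its own windows, and the primary endpoint is not in question here.

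A separate wording conflict concerns unscheduled and repeat data, not ET visits. SAP 7 keeps such data out of subject listings, while SAP 6.1 lists all unscheduled data and SAP 3.9.2 lists all laboratory data, unscheduled visits included. This looks like a drafting slip with no effect on any analysis.

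**What to change.** 1. In SAP 6.1, limit the exclusion of unmapped ET visits to by-visit summaries.
2. State that the any-postbaseline PCS tables (laboratory, vital signs, ECG) and the laboratory shift tables use all on-treatment scheduled and ET values, mapped or not, with denominators defined on the same values.
3. Define on-treatment for these three assessments. The 7-day rule in SAP 3.9.1 covers adverse events only.
4. Summarise the end-of-treatment ECG at the last postbaseline value already defined in SAP 6.1.
5. As a separate wording correction, reconcile SAP 7 with SAP 3.9.2 and 6.1 so that unscheduled and repeat data appear in the listings.

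The cost is a few sentences in the SAP and minor programming. Laboratory and vital-sign PCS percentages may rise slightly. By-visit summaries keep their windowed values.

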6.2. Handling of Partial Dates of Concomitant Medication

Partial start dates of prior and concomitant medications will be assumed to be the earliest possible date consistent with the partial date. Partial stop dates of prior and concomitant medications will be assumed to be the latest possible date consistent with the partial date. In the case of a completely missing stop date, medication will be assumed to be ongoing.

6.3. Handling of Safety Data

All efforts should be made to obtain any missing information from the investigator. For C-SSRS, vital signs, laboratory testing (chemistry, hematology, urinalysis), and 12-lead ECGs, only observed data will be used for analyses, and missing data will not be imputed.

7. GENERAL STATISTICAL METHODOLOGY

In general, summary statistics (n, mean, standard deviation [SD], median, minimum, and maximum for continuous variables, and number and percentage of subjects in each category for categorical variables) will be provided by treatment group. All summary tables will be based on observed data, and missing values will not be imputed unless otherwise indicated. Measurements collected from unscheduled visits or repeated assessments will not be included in the by-visit summary tables or figures, the analyses for the PCS postbaseline values, and subject listings. Source data for the summary tables and statistical analyses will be presented as subject data listings.

7.1. Reporting Precision

Summary statistics will be presented to the following degree of precision, unless otherwise specified:

Table 14: Degree of Precision

Statistics	Degree of Precision
Mean, Median, Confidence limit boundaries	One more than the raw data, up to 3 decimal places
Standard deviation, Standard error	One more than the mean, up to 3 decimal places
Minimum, Maximum	The same as the raw data, up to 2 decimal places
p-value	Rounded to 3 decimal places and therefore presented as 0.xxx; p-values smaller than 0.001 as '<0.001'; p-values greater than 0.999 as '>0.999'
Percentage	One decimal place. A percentage of 100% will be reported as 100%. Percentages of zero will be reported as 0

Fractional numeric values will be presented with a zero to the left of the decimal point (for example, 0.12 – 0.30).

For weight, height, and BMI, one decimal place will be used for summary statistics.

8. PROGRAMMING SPECIFICATIONS

Programming specifications will be provided in a separate document.

9. MOCK TABLES, LISTINGS AND GRAPHS (TLGS)

Mock-up tables and listings will be provided in a separate document.

APPENDIX 1. COVID-19 ANALYSIS

Pandemic has resulted in certain disruptions in the study conduct since early 2020, including site closure, delayed study drug supply, subjects discontinuation and missing assessments. These impacts were limited in scope upon review of the protocol deviations, and also confounded by the initiation of new regions. Sites in Ukraine and Russia were first initiated in March 2020 and July 2020. Therefore, only descriptive statistics will be provided to explore the potential impact of the pandemic on the primary and secondary objectives of the study. The following subgroup analysis (before vs during pandemic) will be conducted:

- Disposition
- Demographics and Baseline Characteristics
- Protocol Deviation
- Primary Efficacy Endpoint
- Key Secondary Endpoints
- TEAE
- SAE

Subjects enrolled before March 1, 2020 will be grouped as before pandemic, and subjects enrolled after this date will be grouped as during pandemic. While the pandemic has started in various regions a few weeks apart, a single cutoff date will be applied, due to the relatively slow enrollment at the time (about 4 subjects/month) and short treatment duration.

APPENDIX 2. ADVERSE EVENTS ASSOCIATED WITH MOVEMENT DISORDERS (INCLUDING EXTRAPYRAMIDAL SYNDROME AND TARDIVE DYSKINESIA)

Preferred Term (SMQ [#20000095] of Extrapyramidal Syndrome)	Preferred Term Code
Abnormal involuntary movement scale	10075002
Action tremor	10072413
Akathisia	10001540
Akinesia	10001541
Athetosis	10003620
Ballismus	10058504
Blepharospasm	10005159
Bradykinesia	10006100
Bradyphrenia	10050012
Buccoglossal syndrome	10006532
Chorea	10008748
Choreoathetosis	10008754
Chronic tic disorder	10076661
Cogwheel rigidity	10009848
Complex tic	10076663
Dopamine dysregulation syndrome	10067468
Drooling	10013642
Dyskinesia	10013916
Dyskinesia neonatal	10013922
Dyskinesia oesophageal	10013924
Dysphonia	10013952
Dystonia	10013983
Dystonic tremor	10073210
Emprosthotonus	10014566
Extrapyramidal disorder	10015832
Facial spasm	10063006
Fine motor skill dysfunction	10076288
Freezing phenomenon	10060904
Gait disturbance	10017577
Gait inability	10017581
Grimacing	10061991

Preferred Term (SMQ [#20000095] of Extrapyramidal Syndrome)	Preferred Term Code
Hyperkinesia	10020651
Hyperkinesia neonatal	10020652
Hypertonia	10020852
Hypertonia neonatal	10048615
Hypokinesia	10021021
Hypokinesia neonatal	10021022
Hypokinetic dysarthria	10082243
Laryngeal tremor	10078751
Laryngospasm	10023891
Meige's syndrome	10027138
Micrographia	10057333
Mobility decreased	10048334
Motor dysfunction	10061296
Movement disorder	10028035
Muscle contractions involuntary	10028293
Muscle rigidity	10028330
Muscle spasms	10028334
Muscle spasticity	10028335
Muscle tightness	10049816
Muscle tone disorder	10072889
Muscle twitching	10028347
Musculoskeletal stiffness	10052904
Oculogyric crisis	10030071
Oesophageal spasm	10030184
On and off phenomenon	10030312
Opisthotonus	10030899
Oromandibular dystonia	10067954
Oropharyngeal spasm	10031111
Parkinsonian crisis	10048868

Preferred Term (SMQ [#20000095] of Extrapyramidal Syndrome)	Preferred Term Code
Parkinsonian gait	10056242
Parkinsonian rest tremor	10056437
Parkinsonism	10034010
Parkinsonism hyperpyrexia syndrome	10071243
Parkinson's disease	10061536
Parkinson's disease psychosis	10074835
Pharyngeal dyskinesia	10070912
Pharyngeal dystonia	10081226
Pleurothotonus	10035628
Postural reflex impairment	10067206
Postural tremor	10073211
Posture abnormal	10036436
Posturing	10036437
Propulsive gait	10082328
Protrusion tongue	10037076
Provisional tic disorder	10076694
Psychomotor hyperactivity	10037211
Rabbit syndrome	10068395
Reduced facial expression	10078576
Respiratory dyskinesia	10057570
Resting tremor	10071390
Restlessness	10038743
Risus sardonicus	10039198
Secondary tic	10076702
Spasmodic dysphonia	10067672
Tardive dyskinesia	10043118
Tic	10043833
Tongue spasm	10043981
Torticollis	10044074
Torticollis psychogenic	10044076
Tremor	10044565
Tremor neonatal	10044575
Trismus	10044684
Uvular spasm	10050908

Preferred Term (SMQ [#20000095] of Extrapyramidal Syndrome)	Preferred Term Code
Walking disability	10053204
Writer's cramp	10072249

Note: The list is based on MedDRA version 24.0 and will be updated based on the dictionary or relevant SMQ updates at the time of the analysis.

